#### **1. Design of the study:**

Double-blinded pretest posttest randomized control design will used.

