#### **2. Subjects:**

The age of participant will range from 30 to 65 years. These patients will be allocated from the outpatient clinic in faculty of physical therapy at Beni-Suef University. The purpose, nature and potential risk of the study will be explained to all participant and they will sign a written informed consent prior to participation (**Appendix I**). Forty patients from both gender will be involved in this study and will randomly subdivided into two equal groups in number:

**Group (A):** (experimental group 1) this group composed of 20 subjects represented the experimental group 1. They will receive 6 sessions acetic acid shockwaves phonophoresis with Time between sessions 5-7 days plus exercise and dietary advice.

**Group (B):** (experimental group 2) this group composed of 20 subjects and represented the experimental group 2 who will receive 6 sessions of Shockwave plus exercise and dietary advice.

**Group (C): (Control Group):** This group composed of 20 subjects they will take conventional physical therapy program (Exercise)

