#### **4. Activity of daily living:**

- Foot and Ankle Ability Measure (FAAM) scale will measure disability: which is a self-report outcome instrument developed to assess physical function for individuals with foot and ankle related impairments. Patient will choose from (0-4) where zero mean unable to do and four mean no difficulty (see appendix II). This instrument includes two subscales:
  - a. Activities of Daily Living (ADLs) subscale of 26 items
  - b. Sports subscale of 8 items

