## **Statistical Analysis:**

- All analysis will be carried out using the statistical package SPSS V.25.00 (IBM Corporation).
- Data will be expressed as mean and SD or median (in case of violation of normality) for continuous variables and as percentages for categorical data.
- The Shapiro-Wilks test will be used to test the normality of the data.
- 2-way mixed Design MANOVA will be used to compare the groups for normally distributed data.
- 2-way mixed Design MANOVA will be used to compare the groups for normally distributed data.
- Kruskal Wallis and Mann-Whitney tests will be used to compare the groups for non-parametric and not normally distributed data.
- Age and gender will be considered as an independent variable.
- Pairwise multiple comparisons will be performed using the Bonferroni correction test.
- All tests are two-sided, and statistical significance will be set at  $p<0.05$ .

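### Between-group tests are not adjusted for each outcome's pretest value, and a normality test with no stated unit decides whether an outcome goes to rank tests that take no covariate

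*Combined protocol and SAP*

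**What the plan says.** The design section states: "Double-blinded pretest posttest randomized control design will used". Under Measurement methods, assessments are planned at pretest, posttest and one-month follow-up. The X-ray subsection asks only for at least one film before and one after treatment.

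The Statistical Analysis section is the whole statistical plan. On this point it contains five elements:

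- a check of distribution: "The Shapiro-Wilks test will be used to test the normality of the data";
- a parametric branch: "2-way mixed Design MANOVA will be used to compare the groups for normally distributed data", with its two factors not named;
- a rank branch: "Kruskal Wallis and Mann-Whitney tests will be used to compare the groups for non-parametric and not normally distributed data", with no word on whether posttest values or changes are ranked;
- further variables: "Age and gender will be considered as an independent variable", tied to no particular model;
- multiplicity: "Pairwise multiple comparisons will be performed using the Bonferroni correction test".

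No outcome's pretest value is named as a covariate here or elsewhere. The plan does not say whether Shapiro-Wilk is applied to raw values, changes or residuals, by arm or pooled, or per visit. It does not say how many failures move an outcome to ranks, or which outcomes count as non-parametric. For the FAAM, "Patient will choose from (0-4) where zero mean unable to do and four mean no difficulty"; whether the resulting score is treated as continuous or ordinal is left open.

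**The concern.** In a small randomised trial, an outcome's own pretest value is usually the most useful covariate, and here it is collected at no extra cost. The plan does not commit to using it in the between-group comparisons.

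The two branches also treat it differently. A mixed MANOVA with time as a factor includes the pretest as one level of the response. Kruskal-Wallis and Mann-Whitney take one response and one grouping factor, so pretest, visit, age and sex have no covariate role. The pretest enters only if the response is a change score.

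Which branch an outcome takes depends on a data-driven test whose unit is undefined. The adjustment behind A versus B, A versus C and B versus C is therefore not settled before the data are seen. At stake are precision and pre-specification.

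**Working it through.** **Inputs from the documents.** Three arms are listed with 20 each (for group A, "this group composed of 20 subjects represented the experimental group 1"); the same section also gives a total of forty in two groups, and 20 per arm is used here. There are three visits and four outcomes, and tests are two-sided at 0.05. Three arms give three pairs, so the planned Bonferroni level is 0.05/3 = 0.0167.

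**Assumptions, because the documents give no figure.** True difference 0.8 SD; pre-post correlation ρ of 0.5 or 0.7 (0.9 where stated); normal or lognormal data; Shapiro-Wilk cut-off 0.05, with any one failing cell triggering the switch. Age and sex effects are not modelled. The plan has no power calculation to reproduce.

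**Step 1: approximate power at 0.05/3, normal data.** Power ≈ Φ(δ/(σ√(2/n)) − z), with δ = 0.8, n = 20, √(2/20) = 0.316 and z = 2.394. The relevant σ is √(1−ρ²) for ANCOVA and √(2(1−ρ)) for change. For ranks on posttest values, σ = 1 and n is multiplied by 3/π.

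- ANCOVA, ρ = 0.5: σ = 0.866, 0.8/(0.866 × 0.316) = 2.92, power 70%. At ρ = 0.7: σ = 0.714, ratio 3.54, power 87%.
- Change-score t-test, ρ = 0.5: σ = 1, ratio 2.53, power 55%. At ρ = 0.7: σ = 0.775, ratio 3.27, power 81%.
- Ranks on posttest: effective n = 19.1, ratio 2.47, power 53% at any ρ.

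**Step 2: simulated power at 0.05/3.** This includes the small-sample loss that the formula ignores; figures carry simulation error of a few points.

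| Normal data | ρ = 0.5 | ρ = 0.7 |
|---|---|---|
| ANCOVA on pretest | 67% | 84% |
| Quade rank ANCOVA | 64% | 78% |
| Mann-Whitney, posttest | 50% | 47% |
| Mann-Whitney, change | 48% | 75% |

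ANCOVA gains 67 − 50 = 17 and 84 − 47 = 37 points over posttest ranks, and 67 − 48 = 19 and 84 − 75 = 9 points over change ranks.

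**Step 3: against the MANOVA branch.** At alpha 0.05, for one outcome and ρ = 0.5/0.7/0.9, ANCOVA gives 81/92/100% and a group-by-time test 74/91/100%: gains of 7, 1 and 0 points. The comparator is a two-degree-of-freedom test for A versus B, not the planned pairwise test, so this gap is only indicative.

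**Step 4: how often the switch fires on perfectly normal data.** One test on pooled residuals: about 5%. Three arms at one visit: 1 − 0.95³ = 14%. All nine arm-by-visit cells: 1 − 0.95⁹ = 37% if independent, 30–37% simulated. At alpha 0.05 and ρ = 0.5/0.7, the switch both fires and changes the A versus B verdict in 4.4/4.4% of trials (three cells) or 11.9/11.5% (nine cells) with posttest ranks. With change ranks the figures are 2.2/1.4% and 5.4/3.4%.

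**Step 5: skewed data.**

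- Mild skew (lognormal, log-SD 0.4), alpha 0.05, ρ = 0.5/0.7: the three-cell switch fires in 76–77% of trials. Power is 77/80% for the switched rule with posttest ranks, 75/90% for change ranks, about 80/90% for ANCOVA and 87/95% for Quade.
- Strong skew (log-SD 0.8), at 0.05/3: posttest ranks 88/88%, ANCOVA 69/82%. At alpha 0.05, Quade reaches 98/99.5% against 95/95% for posttest ranks.

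**Step 6: type I error.** The switched rule rejects in 4.2–5.8% of null trials, close to the nominal 5%.

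**The case against.** The strongest reply is that the plan does not discard the pretest. A group-by-time MANOVA uses it, Mann-Whitney on change scores uses it, and nothing in the plan excludes either. This stands. A reader might infer that the pretest is ignored altogether, or that rank tests cannot use it in any form. The documents support only the narrower statement that it is not a covariate, and that in the rank branch its use is unspecified. The largest losses require posttest ranks, and how often they arise depends on a trigger assumed here.

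A second reply is that rank tests are legitimate and sometimes better. This also stands: under strong skew, posttest ranks beat plain ANCOVA. It is an argument for fixing the method per outcome beforehand and for a rank analysis that uses the pretest. It is not an argument for an undefined switch.

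A third is that the general p<0.05 line supplies the trigger. It could be read as the Shapiro-Wilk cut-off, but it is not tied to the switch, and the unit would still be missing.

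A reader might also infer that the switch inflates false positives. The simulated rates give no support for that.

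**Conclusion.** The point holds as a matter of precision and pre-specification, of minor to moderate severity. Between-group comparisons are not adjusted for the pretest as a covariate, and a normality test without a defined unit can move an outcome to tests that take no covariate.

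If an outcome reaches the rank branch with roughly normal data, the cost at 0.05/3 is about 17 to 37 points of power against ANCOVA when posttest values are ranked, and 9 to 19 when changes are ranked. If it stays in the MANOVA branch with time as a factor, the cost is modest at ρ = 0.5 and close to nil at 0.7 and above.

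The sizes rest on the assumed 0.8 SD difference, correlations and distribution shapes, and on 20 per arm. The gap in the plan's text does not depend on them. Multiplicity across the four outcomes is a separate question and is not part of this point.

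**What to change.** In the Statistical Analysis section:

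1. Stop using Shapiro-Wilk to choose the test.
2. For each outcome, pre-specify one main between-group analysis adjusted for that outcome's pretest value, with age and sex as covariates. Use ANCOVA at posttest, or a mixed model with group, visit and group-by-visit where a one-month value exists. Spur length may have none, given the X-ray subsection.
3. Report the A−B, A−C and B−C differences with 95% confidence intervals, under the Bonferroni correction already planned.
4. For any outcome expected in advance to be strongly skewed, or to be treated as ordinal, name the Quade rank ANCOVA as its main analysis now. Settle the FAAM's status at the same time. For the other outcomes, always report the rank ANCOVA as a fixed sensitivity analysis, replacing the unadjusted rank tests.
5. Keep the mixed MANOVA as the global test, with time named as the within-subject factor and only visits at which all four outcomes are measured.

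This needs no extra patients or measurements. The costs are two results per contrast for some outcomes, so the main one must be labelled beforehand, and a real loss if plain ANCOVA is chosen for an outcome that proves strongly skewed (about 69/82% against 88/88% for posttest ranks at 0.05/3). On normal data, choosing the rank ANCOVA instead costs about 3 points at ρ = 0.5 and 6 at 0.7 (67 − 64 and 84 − 78).

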- $H_0$  : there is no statistical significant effect of the use of extracorporeal acetic acid shockwave phonophoresis on length of calcaneal spur, pain pressure threshold, pain intensity level and physical function in patients with calcaneal spur.
- $H_0$ : there is no statistically significant effect of the use of extracorporeal Shockwave on length of calcaneal spur, pain pressure threshold, pain intensity level and physical function in patients with calcaneal spur.
- $H_0$ : there is no statistically significant difference between extracorporeal shockwave versus acetic acid shockwave phonophoresis on length of calcaneal spur, pain pressure threshold, pain intensity level and physical function in patients with calcaneal spur.

➤ **Definition of terms:**

The following terms defined for clear understanding of the terminology used in the presented study:

**Calcaneal spur:** is an osteophyte outgrowth just medial process of calcaneal tuberosity.

**Shockwave:** is an acoustic wave characterized by high positive pressures of more than 1000 bar (100 MPa), which can be developed within an extremely short rise time ( $10^{-9}$  seconds) and followed by a low-pressure phase of tensile stress equivalent to 100 bar (10 MPa).

**Energy flux density:** is a term used to reflect the amount of energy delivered to a specific area of tissue. measured in (Mj/mm^2) (**Speed C , 2014**)

**Enthesis** is the site of attachment of tendon, ligament, fascia, or capsule to bone.

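### If the trial has three arms, Bonferroni over the group pairs is valid but needlessly conservative for A versus B; a step-down rule keeps the 5% limit per outcome and visit and never rejects fewer pairs

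*Combined protocol and SAP*

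**What the plan says.** The Statistical Analysis section gives one multiplicity rule: "Pairwise multiple comparisons will be performed using the Bonferroni correction test". It adds "All tests are two-sided, and statistical significance will be set at" p<0.05. It does not say which comparisons form the family, and the figure 0.0167 appears nowhere.

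The main test for normal data is "2-way mixed Design MANOVA will be used to compare the groups for normally distributed data". Kruskal-Wallis and Mann-Whitney tests are planned otherwise. Measurement methods (Chapter III, section 6A) sets assessments before treatment, after treatment and one month later.

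The Subjects section (Chapter III, section 2) lists three groups:
- A: "this group composed of 20 subjects represented the experimental group 1"
- B: "this group composed of 20 subjects and represented the experimental group 2 who will receive 6 sessions of Shockwave"
- C: "This group composed of 20 subjects they will take conventional physical therapy program (Exercise"

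The same section opens differently: "Forty patients from both gender will be involved in this study and will randomly subdivided into two equal groups in number".

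The Hypothesis section of Chapter I has one between-group null: "there is no statistically significant difference between extracorporeal shockwave versus acetic acid shockwave phonophoresis on length of calcaneal spur", extended there to pressure pain threshold, pain intensity and physical function. No stated null compares A or B with C. No outcome is named primary, and there is no power calculation.

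**The concern.** Three groups give three pairs, and Bonferroni tests each at one third of 0.05. The one between-group question that the protocol poses therefore pays for two comparisons that it does not pose, and goes on paying after those two have been rejected.

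The three nulls are linked. If one pair of means truly differs, at most one of the other two equalities can be true. Once one pair has been rejected at 0.0167, charging the remaining two at one third of alpha is more than a 5% family-wise limit requires.

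The stake is power for A versus B with 20 per arm. Both arms receive shockwave and differ only in the coupling gel (Therapeutic methods, section B), so this contrast is plausibly small, though the documents do not say so.

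**Working it through.** **Inputs from the documents.** Two-sided alpha 0.05; 20 per group; three groups; Bonferroni for pairwise comparisons.

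**Assumptions.** The documents give no effect size, SD, target power or dropout. I take normal data with a common SD of 1, no dropout, one outcome at one visit, and a range of A-B differences d. The Bonferroni family is taken as the three group pairs within one outcome and visit.

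**There is no figure of the plan's own to reproduce**, since it reports no power or sample-size calculation.

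**Step 1: per-pair level.** 3 groups give 3 × 2 / 2 = 3 pairs, and 0.05/3 = 0.0167.

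**Step 2: the step-down rule.** Test the smallest of the three p-values at 0.05/3. If it is significant, test each of the other two at 0.05.
- All three means equal: a false rejection requires the smallest p-value to be below 0.05/3, which has probability at most 3 × 0.0167 = 0.05.
- Exactly one equality true: only that pair can be falsely rejected, and it is never tested above 0.05.
- Exactly two equalities true: impossible with three means.

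So family-wise error is at most 5%. Any pair with p below 0.0167 is still rejected, so no Bonferroni rejection is lost.

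**Step 3: the ceiling on the gain.** The most that A versus B can gain is the power at 0.05 minus the power at 0.0167. By normal approximation, power = Φ(d√(20/2) − z), with z = 1.960 at 0.05 and 2.394 at 0.0167:

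| d | at 0.05 | at 0.0167 | gap (points) |
|---|---|---|---|
| 0.5 | 35.2% | 20.8% | 14.4 |
| 0.7 | 60.0% | 42.8% | 17.2 |
| 0.8 | 71.6% | 55.4% | 16.2 |
| 1.0 | 88.5% | 77.9% | 10.6 |

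The largest gap is 17.2 points, at d = 0.69. The noncentral t with 57 df gives a maximum of 17.9.

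**Step 4: gain actually reached.** It depends on where C lies. Simulated A-B power (3 × 20, pooled-variance t tests, 57 df, at least 100,000 runs):

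| True means | Bonferroni | Holm | Step-down |
|---|---|---|---|
| A-B 0.8, C midway between A and B | 53% | 54% | 55% |
| A-B 0.8, C = B | 53% | 56% | 61% |
| A-B 0.8, C 0.8 below B | 53% | 66% | 70% |
| A-B 0.7, C 1.5 below B | 41% | 59% | 59% |

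**Step 5: error.** With all means equal, family-wise error is about 4.3% for both Bonferroni and the step-down. With A = B and C 1 SD away, it is about 1.7% for Bonferroni and 5.0% for the step-down. With C 3 SD away, it is again about 1.7% and 5.0%.

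**Step 6: confidence intervals.** An unadjusted 95% interval can exclude zero for a pair that the step-down does not reject. At least one such pair occurs in about 8% of trials when all means are equal, and in about 15% with A-B 0.8 SD and C = B.

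**The case against.** **Bonferroni is valid and standard, so there is no error to correct.** This stands. A reader might infer that the plan's A-B test is wrong or that its error rate is out of control. The documents support neither; the planned rule is on the safe side.

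**The extra power is not free.** This also stands. A reader might infer that Bonferroni buys nothing for the power it gives up. In fact its actual error with A = B and C apart is about 1.7% rather than 5%. That slack matters because the plan has four outcomes, two post-baseline visits, no primary outcome and no correction across them. As an illustration, assume independent tests, A = B and C far away. The chance of at least one false A-B claim over 4 × 2 = 8 tests is 1 − (1 − 0.0167)^8 = 12.6% under Bonferroni and 1 − 0.95^8 = 33.7% under the step-down. Correlation would lower both figures. Neither rule controls error at this level, but Bonferroni's shortfall is smaller.

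**The family is an assumption.** Correct. The design has three assessments, and the first two nulls concern each treatment's own effect, so the Bonferroni bullet may also be meant for comparisons over time. Replacing it outright would remove that protection.

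**The number of arms is unsettled.** Correct. With two arms there is a single group pair and nothing to adjust.

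**If A versus B is the only between-group question, naming it the sole primary contrast at 0.05 needs no gate.** True: with A-B 0.8 SD and C = B, power is 70% tested alone and 61% by step-down. But that gives A versus B a status that the plan has not given it, while the step-down treats the three pairs alike.

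**Rank tests and the full model were not simulated.** Correct. For Mann-Whitney pairs the linkage needs nulls of identical distributions. The simulations also leave out the mixed MANOVA and the age and gender terms.

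**Conclusion.** This is a cheap improvement, not an error. If the trial has three arms, Bonferroni over the group pairs tests A versus B at 0.0167 when a step-down rule gives the same 5% guarantee per outcome and visit and never rejects fewer pairs.

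A reader might take 17 points as the expected gain. It is a ceiling: it needs an A-B difference near 0.7 to 0.8 SD and a well-separated C, and it falls to about 2 points if C lies midway. The documents give no effect sizes from which to choose within that range.

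The conclusion rests on exactly three groups and on a family made up of the three group pairs within one outcome and visit. The power figures also rest on 20 analysed per arm and on roughly normal data with a common SD.

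**What to change.** 1. Reconcile the Subjects section first: forty patients in two groups, or three groups of 20 (60 in all). With two arms, the rest of this point falls away.
2. Keep the Bonferroni bullet for any within-group comparisons over time, and say that this is its scope.
3. Add for the group pairs: *Within each outcome and visit, A-B, A-C and B-C are tested by step-down: the smallest unadjusted p-value against 0.05/3; if significant, each of the other two against 0.05.* Holm (0.05/3, then 0.05/2, then 0.05, stopping at the first non-significant result) is a simpler alternative that also never rejects fewer pairs than Bonferroni, though it usually gains less. Choose one before the data are seen.
4. Label the 95% confidence intervals for the pairs as unadjusted, and say that they can exclude zero where the step-down does not reject. Bonferroni-adjusted intervals may be reported alongside.
5. State that error is controlled per outcome and visit only, not across the four outcomes and two post-baseline visits.

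The cost is a few sentences of analysis-plan wording and a hand comparison of three unadjusted p-values (the LSD option in SPSS, or plain Mann-Whitney). No extra patients are needed. What is given up is the error slack described above and a set of simultaneous intervals that matches the tests.

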## Appendix II

### Foot and Ankle Ability Measure (FAAM) Activities of Daily Living Subscale

Please Answer every question with one response that most closely describes your condition within the past week.

If the activity in question is limited by something other than your foot or ankle mark "Not Applicable" (N/A).

|   | No
Difficulty         | Slight
Difficulty     | Moderate
Difficulty   | Extreme
Difficulty    | Unable
to do          | N/A                      |
|---|--------------------------|--------------------------|--------------------------|--------------------------|--------------------------|--------------------------|
| Standing                                |  |
| Walking on even
Ground               |  |
| Walking on even ground
without shoes |  |
| Walking up hills                        |  |
| Walking down hills                      |  |
| Going up stairs                         |  |
| Going down stairs                       |  |
| Walking on uneven ground                |  |
| Stepping up and down curbs              |  |
| Squatting                               |  |
| Coming up on your toes                  |  |
| Walking initially                       |  |
| Walking 5 minutes or less               |  |
| Walking approximately
10 minutes     |  |
| Walking 15 minutes or
greater        |  |

**Foot and Ankle Ability Measure (FAAM)**  
**Activities of Daily Living Subscale**  
**Page 2**

Because of your foot and ankle how much difficulty do you have with:

|   | No
Difficulty
at all | Slight
Difficulty     | Moderate
Difficulty   | Extreme
Difficulty    | Unable
to do          | N/A                      |
|---|----------------------------|--------------------------|--------------------------|--------------------------|--------------------------|--------------------------|
| Home responsibilities                               |    |  |  |  |  |  |
| Activities of daily living                          |    |  |  |  |  |  |
| Personal care                                       |    |  |  |  |  |  |
| Light to moderate work
(standing, walking)       |    |  |  |  |  |  |
| Heavy work
(push/pulling,
climbing, carrying) |    |  |  |  |  |  |
| Recreational activities                             |    |  |  |  |  |  |

How would you rate your current level of function during you usual activities of daily living from 0 to 100 with 100 being your level of function prior to your foot or ankle problem and 0 being the inability to perform any of your usual daily activities.

— — — . 0 %

